The reasons for discontinuing treatment will be properly documented by the research team and, in case the study is closed, the researchers will ensure the continuity of the medical and hospital assistance to the participant.

If COVID-19 is not confirmed by RT-PCR within 72 hours of the inclusion, the patient will be withdrawn from the study.

Randomization and study arms

Participants will be divided in two groups and randomized 1:1. In this way, they will receive a sequential inclusion number from an electronically drawn number table and will receive the treatment according to the allocation in one of the groups:

Group 1 - Control: Nebulization with 10mL of 0.9% saline solution, administered every 4 hours for 7 days, except the nebulization that would be administered between 12pm and 6 am (5 inhalations per day).

Group 2 - Experimental: Nebulization with enriched heparin (250 μ g/mL diluted in 10mL of 0.9% saline solution), administered every 4 hours, for 7 days, except the nebulization that would be administered between 12 pm and 6 am (5 inhalations per day).

The randomization list will be prepared by an independent statistician, using Stat Trek, a program to construct random number tables, available at <http://stattrek.com/Tables/Random.aspx>. Fifty positions will be drawn in a random and consecutive manner. The envelope containing the randomization will be kept in possession of an independent professional (pharmacist), so that the members of the study team will not know the order of allocation.

Blinding

The clinical trial will be triple-blind. Participants, researchers, the data and statistical analysis team will not have access to the allocation numbers. A pharmacist will produce the heparin and the placebo and will assign a researcher of the team to distribute the product to each participant, according to the randomization list. In addition, presentation of the preparation to the control and experimental group will be identical, since enriched heparin is colorless and odorless to the human eye and nose, as well as the saline solution. The blinding code will not be broken until all research participants have completed the study and the database is closed, that is, it will not undergo further changes. In an emergency, and if necessary, members of the data and security monitoring committee can request a blinding break, only for the participant at risk.

Sample size, recruiting and statistical analysis

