The total recruitment size will be 50 participants, aiming at 40 patients followed during the study period. The sample was estimated considering the number of patients diagnosed as COVID-19 at the São Paulo State University (UNESP) Clinical Hospital that met the study's eligibility criteria.

The sample calculation of 40 patients took into account two independent study arms, with an estimated proportion in the viral load reduction rate of 30% for group 1, that will receive placebo, and 75% for group 2 that will be treated with enriched nebulized heparin as proposed in this study, considering 80% test power and a 5% significance level for a bilateral test.

Categorical variables will be evaluated with Fisher's exact test, continuous variables will be compared with non-parametric methods such as Mann-Whitney test or U test, paired comparisons will be evaluated with the Wilcoxon test, multivariate analyzes will be evaluated with regression Cox analysis and long-term clinical analyzes will be compiled on Kaplan-Meir curves.

Interventions and inpatient schedule

Intervention	Day 0	Day 1	Day 2	Day 3	Day 4	Day 5	Day 6	Day 7	Day 8
Informed consent form	X								
Medical visit, patient story and physical examination	X	X	X	X	X	X	X	X	X
Vital signs assessment	X	X	X	X	X	X	X	X	X
Medications in use	X	X	X	X	X	X	X	X	X
Inclusion and exclusion criteria	X								
COVID-19 viral load in RT-qPCR	X		X			X		X	X
Complete blood count, D-dimer, aPTT, urea, creatinine, glucose, reactive protein C, blood gas and amylase	X		X			X		X	X
Computed thoracic tomography	X								X
HMWH or placebo administration		X	X	X	X	X	X	X	X
Adverse events	X	X	X	X	X	X	X	X	X
Discontinuation criteria	X	X	X	X	X	X	X	X	

Table 1. Schedule for assessments and intervention. The participants will be followed up and evaluated on days 0, 1, 2, 3, 4, 5, 6, 7 and 8 days after randomization.

The closure assessment will be carried out on day 8. Extra data can be collected if the patient's clinical condition changes. Randomization will be performed in up to 24 hours after admission. After the end of the study, the participant will be referred and accompanied at the COVID-19 outpatient clinic São Paulo State University (UNESP) Clinical Hospital.

Adverse events

Adverse effects related to the nebulized use of heparins will be tracked and analyzed according to the Common Terminology Criteria for Adverse Events (CTC-AE 5.0),²⁵ and will be graded from 1 to 5, accordingly to the severity of the event.

Grade	Description

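### The 80% power stated for 40 patients is not delivered by the planned Fisher's exact test, which has about 73% at 20 per arm

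*Combined protocol and SAP*

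**What the plan says.** All the statistical text is in the section on sample size, recruiting and statistical analysis.

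- **Size:** "The total recruitment size will be 50 participants, aiming at 40 patients followed during the study period".
- **Basis of the calculation:** "The sample calculation of 40 patients took into account two independent study arms". The control-arm figure appears as "an estimated proportion in the viral load reduction rate of 30% for group 1, that will receive placebo"; the corresponding figure in the heparin arm is 75%.
- **Error rates:** "considering 80% test power and a 5% significance level for a bilateral test".
- **Test:** "Categorical variables will be evaluated with Fisher's exact test". Continuous variables go to the Mann-Whitney test. No other method for comparing two proportions is named.

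The section on randomization and study arms gives the allocation: "Participants will be divided in two groups and randomized 1:1". Forty patients therefore means 20 per arm. The plan does not say which formula or test produced the 40.

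**The concern.** A power figure belongs to a particular test. The sized comparison is a difference between two proportions, and the plan's rule for categorical data sends it to Fisher's exact test. With 20 patients per arm that test rejects a true null hypothesis much less often than 5% of the time, and it loses power as a result. If the 40 was derived for a less conservative test, the 80% is not a property of the planned analysis.

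This is the only power statement in the plan, and viral load is a primary efficacy objective. A non-significant result would be read against a claimed 20% risk of missing the assumed effect when the actual risk is higher.

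**Working it through.** **Inputs.** Control rate p1 = 0.30, experimental rate p2 = 0.75, two-sided 5% level, 80% power, and 40 followed patients, all from the sample-size section. Allocation is 1:1, from the randomization section, so n = 20 per arm.

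**Step 1: reproduce the plan's 40.** The pooled normal approximation without continuity correction is

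n per arm = [1.960 × √(2 p̄(1 − p̄)) + 0.8416 × √(p1(1 − p1) + p2(1 − p2))]² / (p2 − p1)²

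with p̄ = (0.30 + 0.75)/2 = 0.525. The two terms are 1.960 × √0.49875 = 1.384 and 0.8416 × √(0.21 + 0.1875) = 0.531. Then (1.384 + 0.531)² / 0.45² = 18.1, so 19 per arm or 38 in total. That is within two patients of 40. The continuity-corrected formula gives 22.3, so 23 per arm or 46 in total, and does not reproduce it. The stated size is thus consistent with an uncorrected chi-square calculation.

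**Step 2: power of the named test.** Let X and Y be the responder counts in the two arms, with X ~ Bin(20, 0.30) and Y ~ Bin(20, 0.75). Power is the sum of P(X = a)·P(Y = b) over those of the 21 × 21 possible tables that the test rejects. The maximum type I error is the largest value of the same sum when both arms share one rate, taken over a grid of rates.

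| Test, 20 per arm | Power, 30% vs 75% | Maximum type I error |
|---|---|---|
| Fisher, two-sided p ≤ 0.05 | 73.1% | 2.5% |
| Uncorrected chi-square | 82.3% | 5.3% |
| Boschloo (rejects when Fisher p ≤ 0.0915) | 81.6% | 4.6% |

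Defining the two-sided Fisher p-value by doubling the one-sided value also gives 73.1%. The chance of missing the assumed effect is 100 − 73.1 = 26.9%.

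**Step 3: size at which Fisher reaches 80%.**

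| Per arm | 19 | 20 | 21 | 22 | 23 | 24 | 25 |
|---|---|---|---|---|---|---|---|
| Fisher power | 74.6% | 73.1% | 75.7% | 79.5% | 82.8% | 85.7% | 88.1% |

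The first size to reach 80% is 23 per arm, or 46 evaluable patients.

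**Step 4: sensitivity to the split and to losses.**

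- *Uneven splits of 40 (placebo/heparin):* 19/21 gives 74.9%, 21/19 gives 75.9%, 18/22 gives 75.7% and 22/18 gives 76.3%. All are below 80%.
- *All 50 recruits evaluable:* 25 per arm gives 88.1%.
- *All 50 analysed, with losses counted as failures:* assume the planned loss of 10 in 50 (20%) falls equally on both arms. The rates become 0.30 × 0.8 = 24% and 0.75 × 0.8 = 60%, and Fisher at 25 per arm gives 68%.

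**The case against.** The strongest objection is that the link to Fisher's test is inferred. The plan assigns that test to categorical variables in general and does not name the test for viral load. The primary objective is a sequential RT-PCR assessment, the laboratory form has a field for quantitative viral load, and no responder threshold or time point is defined. Viral load might therefore be analysed by Mann-Whitney, and the phrase describing the 30% and 75% could even mean an average percentage reduction. This ambiguity is real, but it does not save the stated power. If Mann-Whitney is used, a two-proportion calculation says nothing about its power, and the plan gives no standard deviation from which to work it out. The binary reading is also the one that reproduces the 40.

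Second, 73.1% is a low point in Fisher's uneven power curve, and nothing in the randomization section guarantees a 20/20 split. That stands as a qualification: over the splits checked, the risk of a miss runs from about 24% to 27%. None reaches 80% power.

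Third, the input rates are unsourced guesses. Fisher at 20 per arm would have 80.3% power with 78% in place of 75%, or 81.5% with 26% in place of 30%. This shows how soft the inputs are. It does not make the statement true at the rates the plan chose.

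Fourth, this is a small phase I/II study whose main stated intention is safety. Fisher's conservatism creates no excess of false positives, and 50 patients are to be recruited. All true, but the plan ties its 80% to the 40 followed. It also expects losses, including withdrawal of patients whose infection is not confirmed by RT-PCR within 72 hours.

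**Conclusion.** The concern holds. At the plan's own rates, significance level and 40 followed patients, the named test has 73.1% power, about 7 points below the stated 80%. The risk of missing the assumed effect is about 27% rather than 20% at 20 per arm, and at least about 24% for the uneven splits examined. The figure of 40 is sound for an uncorrected chi-square test. The fault is the mismatch between that calculation and the planned analysis.

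The 73.1% assumes that viral-load response is compared as a yes/no outcome with plain two-sided Fisher at 20 per arm. If it is not compared that way, the 80% describes no planned test and still needs correcting. The statement is wrong as written and should be fixed, although it causes no bias and no inflation of type I error.

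**What to change.** Keep the sample size and make one of two changes in the sample-size and analysis section.

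1. **Keep Fisher and restate the power:** about 73% for 40 evaluable patients (20 per arm) at 30% versus 75%, two-sided 5%.
2. **Name Boschloo's unconditional exact test** for the viral-load responder comparison. Its power is 81.6% at 20 per arm with maximum type I error of 4.6%, so the 80% statement becomes true with no extra patients.

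The second option is credible only if it is recorded before unblinding. If the code has already been broken, the first is the one to use. In either case the text should say that the 80% or 73% refers to the responder comparison. That requires a definition of response and a time point, which the plan now lacks.

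The power or test correction itself is one sentence. The only cost of the first option is a less favourable stated power. Keeping both Fisher and 80% would instead need 46 evaluable patients, or 46/0.8 = 57.5, so 58 recruits at the plan's own 40-in-50 retention. That is not necessary.

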A study carried out by Bendstrup, et al (2002),¹⁷ evaluated the effects of the inhibition of systemic coagulation through nebulized unfractionated heparin at doses up to 64 mg and identified that there is a dose-dependent effect for factor Xa inactivation, inducing minimal changes in aPTT, and it is safe for clinical or research purposes, without increasing the risk of bleeding.¹⁸

Phelps, et al (2020),¹⁹ carried out a systematic review on the use of UFH inhalation for the treatment of inhalation injury caused by heat in burn patients and concluded that nebulized heparin did not demonstrate an increase in the risk of bleeding rates and decreased the duration of mechanical ventilation.

For COVID-19, the heparin anti-viral effect is expected to be related to the fact that heparin blocks viral interaction with host receptors thereby inhibiting virus interaction with the cell and, consequently, viral invasion.^{20, 21} To this moment, some studies indicate that treatment with systemic heparin reduced hospital mortality in patients with COVID-19²² and a previous study that strongly supported the clinical investigation of heparin as a potential treatment for patients with COVID-19,^{23, 24} justifies further investigation to prove these clinical effects.

Objectives

Primary objectives assessment

Safety: related to the use of nebulized enriched heparin by patients with SARS-CoV-2 through the assessment of hemorrhagic events of any nature, alteration of the coagulation testing, like prolonged activated partial thromboplastin time (aPTT), indicated by an increase in aPTT>1.5, and heparin-induced thrombocytopenia; Efficacy: related to the proposed treatment, through analysis of the SARS-CoV-2 viral load of the participants treated by the sequential assessment of reverse transcription-polymerase chain reaction (RT-PCR) in the nasal swab.

Secondary objectives assessment

Safety measured by respiratory, clinical, laboratorial and tomographic findings as follows, in number of patients, and hospitalization days:

Supplemental oxygen therapy needed;

Mechanical pulmonary ventilation needed;

Renal failure development;

Development of major cardiovascular events such as pulmonary embolism and acute myocardial infarction;

Demand for intensive care unit (ICU) treatment;

Secondary pulmonary bacterial infections (bacterial pneumonia);

Deep vein thrombosis (DVT) through Doppler ultrasonography assessment;

Pancreatitis characterized by increase in amylase >200 U/L;

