Demand for corticosteroid therapy such as hydrocortisone, dexamethasone and other corticosteroids due to inflammatory pulmonary disease;

Death;

Increase in white blood cell count (>10.000 cells/mm³);

Increase in C reactive protein test (CRP) (>3.00mg/L);

Deterioration of arterial blood gas paO₂/pFiO₂ ratio (<200);

Altered sodium (< 135mEq/L or > 145mEq/L);

Altered potassium (< 3,5mEq/L or > 5,5mEq/L);

Worsening of pulmonary area compromised (%) by inflammation or infection through tomographic assessment.

Method

EnHanCed study design

The present protocol refers to a phase I / II, prospective, randomized, parallel, triple blind clinical trial. This design is justified by the lack of a drug-specific cost-efficient treatment for SARS-CoV-2 patients. The use of a therapeutic drug justifies the need for a placebo control group. A minimum number of participants will be allocated to this study, as the main intention will be to evaluate the safety of the treatment. Triple blind clinical studies have the lowest levels of bias and, therefore, the highest level of evidence for a clinical study. It is understood that there is no need for a purely phase I study based on the literature data previously presented.

The study will be carried out at the São Paulo State University (UNESP) Clinical Hospital of the Botucatu Medical School, Botucatu, São Paulo, Brazil.

Dosage and administration

Considering the pulmonary water loss of 8 to 10mL during the gas exchange in 30 minutes (of inhalation) and compensating the dilution of the solution in the pulmonary fluids, we opted for the dose of 2.5 mg heparin in 10mL of 0.9% saline solution, aiming the effective mean tested doses (62.5 μ g/mL to 250 μ g/mL), nebulized 4/4 hours, except the nebulization that would be administered between 12 pm and 6 am. The treatment will be administered for 7 days because it will be assumed that the reduction in viral load promoted by enriched heparin will have a significant impact during the first 14 days of the infectious process. Considering that the patient has already had the disease for at least seven days when admitted and that the viral load tends to reduce spontaneously after the referred period, it is known that complications persist due to other factors such as inflammatory response.

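### Safety is the trial's main aim, but bleeding and the other primary safety events are compared between arms only by Fisher's exact test, with no interval for the risk, at a sample size set by viral load

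*Combined protocol and SAP*

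**What the plan says.** The study design section gives safety as the reason for the small size: "A minimum number of participants will be allocated to this study, as the main intention will be to evaluate the safety of the treatment". The primary objectives list safety first, assessed "through the assessment of hemorrhagic events of any nature" together with coagulation change and thrombocytopenia, "indicated by an increase in aPTT>1.5, and heparin-induced thrombocytopenia". All three components are worded as events or a threshold, so each patient either has one or does not.

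The section on sample size and statistical analysis plans as follows: "The total recruitment size will be 50 participants, aiming at 40 patients followed during the study period". The 40 is justified by viral-load reduction in 30% of the placebo arm and 75% of the heparin arm, with 80% power and a two-sided 5% level. No safety rate enters the calculation.

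For analysis, the same section says "Categorical variables will be evaluated with Fisher's exact test" and "continuous variables will be compared with non-parametric methods such as Mann-Whitney test or U test". It adds Wilcoxon for paired comparisons, Cox regression and Kaplan-Meier curves. It names no confidence interval, no bleeding rate to be excluded and no population for safety.

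The Adverse events section adds CTC-AE 5.0 grading, a list of items to be examined for each event (type, timing, last administration, causal link, severity), reporting of severe effects to an independent committee, and a discontinuation statement for heparin-related effects of grade 3 or more.

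**The concern.** A Fisher p-value asks whether the data contradict equal event rates. The safety question in a small first study is different: how large an excess of bleeding is still compatible with what was seen? With about 20 patients per arm these two can diverge badly. Four bleeds on heparin and none on placebo would be reported as not significant, although the data would be compatible with an excess of about 40 percentage points.

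At stake is the answer to the trial's declared main question. If the plan is followed literally, the between-arm safety result for each component is a p-value. For moderate true rates that p-value will usually exceed 0.05 whether or not heparin causes harm. Without a prespecified estimate and interval, the report need not show how much harm remains possible.

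**Working it through.** **Inputs from the documents.** 50 recruited and 40 followed, randomised 1:1. That is 40/2 = 20 per arm followed and 50/2 = 25 per arm recruited, assuming an even split. Test: Fisher's exact test. Level: two-sided 5%, which the documents attach to the viral-load calculation and which is carried over here as an assumption. No bleeding rate is given, so all rates below are assumed and shown as a range.

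**The plan's own figure.** With p1 = 0.30, p2 = 0.75 and mean 0.525, the usual normal formula gives n per arm = [1.96·√(2·0.525·0.475) + 0.842·√(0.30·0.70 + 0.75·0.25)]² / 0.45² = (1.384 + 0.531)² / 0.2025 ≈ 18.1, so 19 per arm or 38 in total. This is within two patients of the stated 40 and confirms that the size rests on viral load alone.

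**Smallest significant table.** Against zero control events at 20 per arm, the two-sided Fisher p-value for x heparin events is 2·C(20,x)/C(40,x).
- x = 4: 2·4845/91390 = 0.106
- x = 5: 2·15504/658008 = 0.047

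So 5/20 vs 0/20 is needed. With one control event, 7/20 is needed. At 25 per arm, 5/25 vs 0/25 gives p = 0.0502, so 6/25 is needed.

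**Power.** With a true control rate of 0%, power at 20 per arm is simply P(X ≥ 5) for X ~ Binomial(20, p). With other control rates, the binomial probabilities of all tables with p ≤ 0.05 are summed.

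| Heparin vs control (assumed) | Power, 20 per arm | Power, 25 per arm |
|---|---|---|
| 5% vs 0% | 0.3% | 0.1% |
| 10% vs 0% | 4.3% | 3.3% |
| 10% vs 5% | 1.7% | 1.3% |
| 15% vs 0% | 17% | 16% |
| 15% vs 5% | 7% | 7% |
| 20% vs 5% | 17% | 20% |
| 20% vs 0% | 37% | 38% |
| 30% vs 0% | 76% | 81% |
| 40% vs 0% | 95% | 97% |

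Non-significance is one minus power. At a true heparin rate of 10% and 20 per arm it is 95.7% (control 0%) or 98.3% (control 5%). At 15% it is between 83% and 93%. To reach 80% power at 20 per arm, the true heparin rate must be about 32% with control at 0%, or about 45% with control at 5%.

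**What an interval would show.** The Clopper-Pearson two-sided 95% upper limit after zero events is 1 − 0.025^(1/n).
- 0/20: 16.8%
- 0/25: 13.7%
- 1/20: 0.1% to 24.9%
- 2/20: 1.2% to 31.7%

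For 4/20 vs 0/20, the Wilson limits are 8.1% to 41.6% and 0% to 16.1%. Newcombe's interval for the difference is then:
- lower: 0.20 − √[(0.200 − 0.081)² + 0.161²] ≈ −0.1 percentage points
- upper: 0.20 + √[(0.416 − 0.200)² + 0²] ≈ 41.6 percentage points

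The p-value of 0.106 reports none of this.

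**The case against.** Four objections deserve an answer.

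First, safety does not rest on p-values alone. The Adverse events section plans CTC-AE grading, case-by-case causality review, predefined bleeding events and committee reporting. This stands, and a reader who inferred that Fisher's test is the whole safety analysis would be wrong. These provisions protect patients and describe cases, but none gives a between-arm risk with its uncertainty. Fisher's test is the only named method for comparing the primary safety proportions.

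Second, aPTT and platelets can be analysed as continuous variables. The laboratory form records platelet count and normalised aPTT ratio as numbers, Table 1 schedules the blood count and aPTT on Days 0, 2, 5, 7 and 8, and Mann-Whitney and Wilcoxon are named for such data. This largely stands, so no gap is claimed there. It does not help with haemorrhage or thrombocytopenia counted as events.

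Third, small phase I/II trials are rarely powered for safety. That is true, and the point does not ask for more patients. Low power is the reason to estimate rather than test.

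Fourth, nothing in the documents says that a non-significant result will be read as proof of safety, and intervals can be computed later from reported counts. Both are correct. The point is therefore a prespecification gap, not a charge that the sponsor intends a misleading reading.

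**Conclusion.** The point holds as a gap in estimation and reporting for the trial's main aim. Under the assumed rates, with 20 or 25 per arm and a two-sided 5% level, a non-significant Fisher result is at least 95% likely for true heparin event rates up to about 10% with control at 0-5%. Such a result cannot support a conclusion of safety, and even zero events leaves true rates up to 16.8% (0/20) or 13.7% (0/25) open.

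A reader might go further and infer that non-significance is near-certain whatever the true bleeding rate. The calculation does not support that: at 20 per arm the test detects 30% vs 0% with 76% power and 40% vs 0% with 95%. The weakness concerns moderate excesses, not very large ones. Because the documents state neither an expected nor an unacceptable bleeding rate, they do not settle which part of that range matters clinically.

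**What to change.** Make estimation the primary safety analysis in the statistical section:

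- For any haemorrhage, aPTT>1.5 and heparin-induced thrombocytopenia separately, report the count and rate per arm with Clopper-Pearson 95% limits, and the risk difference with a 95% interval (for example Newcombe).
- Define the safety population as all patients who received at least one nebulisation. This should include those later withdrawn because RT-PCR did not confirm COVID-19 within 72 hours: Table 1 starts administration on Day 1, so they may already have been exposed.
- State that a non-significant Fisher p-value will not be read as evidence of safety, and keep these p-values as descriptive.

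The cost is a short paragraph and a few table columns, with no extra patients or assessments. The downside is that the report must show wide limits, which is an accurate picture of what a trial of this size can say.

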Aphasia	Yes 	No 	
Aphasia start date (blank if not present)			
Aphasia end date (blank if still present)			
Hyporexia	Yes 	No 	
Hyporexia start date (blank if not present)			
Hyporexia end date (blank if still present)			
Heart rate (BPM)			

Brachial systolic pressure (mmHg)					
Brachial diastolic pressure (mmHg)					
Peripheral oxygen saturation (%)					
Axillary temperature (Celsius)					
Paleness	Normal 	1+/4+ 	2+/4+ 	3+/4+ 	4+/4+ 
Cyanosis	Normal 	1+/4+ 	2+/4+ 	3+/4+ 	4+/4+ 
Oral cavity	Normal 	Altered 			
Description					
Pulmonary auscultation	Normal 	Altered 			
Description					
Cardiac auscultation	Normal 	Altered 			
Description					
Abdominal examination	Normal 	Altered 			
Description					
Limbs (pulses, edema, skin conditions)	Normal 	Altered 			
Description					

Figure 2. Clinical assessment and physical examination form based on SARS-CoV-2 most prevalent symptoms.

Laboratory results and tomographic findings form			
Form Number:	Date:		
RT-qPCR	Positive 	Negative 	
RT-qPCR quantitative viral load			
Blood count	Normal 	Altered 	
Hemoglobin (g / dL)			
Hematocrit (%)			
Mean corpuscular volume (fL)			
Red cell distribution width (%)			
Platelets count (10³ / µL)			
White cell count (10³ / µL)			
Neutrophils (%)			
Lymphocytes (%)			
Bands (%)			
Arterial gas	Normal 	Altered 	
pH			
pCO₂ (mmHg)			
PaO₂ / FiO₂			
HCO₃ (mEq / L)			
SO₂ (%)			
Base Excess			
D-Dimer (µg / mL)			
aPTT	Normal 	Altered 	
Prothrombin time (PT)			
International normalized ratio (INR)			
Activated partial thromboplastin time (aPTT)			
Normalized aPTT Ratio			
Renal function	Normal 	Altered 	
Urea (mg / dL)			
Creatinine (mg / dL)			

Fasted glucose (mg / dL)	
C reactive protein (CRP) (mg / L)	
Amylase (U / L)	
Thoracic tomography description	

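### The primary viral-load analysis fixes no swab day, no definition of reduction and no stated use of the Day 0 value; one named Day 0-adjusted test would close the gap

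*Combined protocol and SAP*

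**What the plan says.** Under Primary objectives assessment, efficacy rests on nasal swabs and is judged "through analysis of the SARS-CoV-2 viral load of the participants treated by the sequential assessment of reverse transcription-polymerase chain reaction". Table 1 has a row for "COVID-19 viral load in RT-qPCR" with marks on Days 0, 2, 5, 7 and 8. The laboratory form has a field for "RT-qPCR quantitative viral load" beside the positive/negative result, so a number is recorded each time.

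The section Sample size, recruiting and statistical analysis assumes "two independent study arms, with an estimated proportion in the viral load reduction rate of 30% for group 1"; the heparin arm is put at 75%, with 80% power and a two-sided 5% level. On numbers, the same section states: "The total recruitment size will be 50 participants, aiming at 40 patients followed during the study period".

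The analysis text is one sentence, sorted by type of variable. It assigns Fisher's exact test to categorical data. The entry for continuous data reads: "continuous variables will be compared with non-parametric methods such as Mann-Whitney test or U test". For within-patient comparisons and adjusted models, the plan has only this: "paired comparisons will be evaluated with the Wilcoxon test, multivariate analyzes will be evaluated with regression Cox analysis". Kaplan-Meier curves are kept for longer-term outcomes. None of these is tied to viral load, to a day or to the Day 0 value.

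**The concern.** Three things needed to run the primary efficacy analysis in only one way are missing: which of the four post-baseline swabs counts, what a reduction is (threshold, reference day, undetectable values), and how the Day 0 value enters the comparison between arms. Of the listed methods, only the paired Wilcoxon test by its form compares with an earlier value, and it works within an arm. Dosage and administration expects viral load to fall by itself after the first week, so a within-arm fall is not evidence of a drug effect. Cox regression is for time to an event and does not adjust a continuous viral load.

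Two things are at stake. If the day and test are chosen after the data are seen, the 5% level is not protected. And with about 20 patients per arm, power depends strongly on whether the raw value, the change, a responder or a Day 0-adjusted value is tested.

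**Working it through.** **1. The plan's own figure.** Inputs from the sample-size paragraph: 30%, 75%, two-sided 5%, 80% power, two equal arms. The pooled normal formula gives

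n = [1.96·√(2·0.525·0.475) + 0.842·√(0.3·0.7 + 0.75·0.25)]² / 0.45² = (1.384 + 0.531)² / 0.2025 ≈ 18.1, so 19 per arm, 38 in all.

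The stated 40 agrees to within 2, and 40/0.8 = 50 recruited.

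**2. The same contrast with the listed test.** Summing exact binomial probabilities over all tables with a two-sided Fisher p ≤ 0.05 gives 73.1% power at 20 per arm, 82.8% at 23 (the first size above 80%) and 88.1% at 25. If a missing swab counts as no reduction, the rates shrink in proportion. With 10% missing they are 27% vs 67.5% and power at 20 per arm is 62%. With 20% missing they are 24% vs 60%, and power is 52% at 20 per arm or 68% at 25.

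**3. Why a threshold is needed.** If reduction meant any fall from Day 0, the placebo rate by Day 7 would be Φ(7·d / (SD·√(2(1−ρ)))), where d is the daily decline and ρ the correlation of the Day 7 with the Day 0 value. The documents give none of these. Assume d 0.05-0.2 log10 per day, SD 1.0-1.5 log10, ρ 0-0.7.
- Lowest: 0.35/(1.5·1.414) = 0.165, or 57%.
- Highest: 1.4/(1.0·0.775) = 1.81, or 96%.

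Neither is near 30%.

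**4. False positives if every swab were tested.** Four independent tests: 1 − 0.95⁴ = 18.5%. Simulated raw Mann-Whitney tests at 20 per arm with no drug effect (20,000 trials, Monte Carlo error at most 0.4 point) give 18.1%, 17.4%, 16.1%, 13.8% and 9.7% for a correlation between swabs of 0, 0.3, 0.5, 0.7 and 0.9. One pre-chosen test gives about 5%.

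**5. Power of one test at one swab.** Assumed: uniform 1.0 log10 shift, normal log10 values, 20 per arm. Rank ANCOVA is the regression of the pooled follow-up rank on the Day 0 rank and arm. Its null rejection rate was within 4.6-5.4%.

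| ρ with Day 0 | Raw Mann-Whitney (SD 1.0 / 1.5) | Rank ANCOVA (SD 1.0 / 1.5) | Gain, points |
|---|---|---|---|
| 0 | 85.0% / 51.1% | 84.3% / 50.8% | nil |
| 0.3 | 84.9% / 51.2% | 87.0% / 54.1% | 2-3 |
| 0.5 | 85.1% / 51.3% | 92.1% / 61.5% | 7-10 |
| 0.7 | 84.7% / 51.3% | 98.1% / 76.6% | 13-25 |

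The comparison with Mann-Whitney on change follows from the spread of change, SD·√(2(1−ρ)).
- At ρ 0.3 this is 1.18 SD, wider than the raw value. Power is about 72% against 87% for rank ANCOVA (SD 1.0).
- At ρ 0.5 it equals SD, so change has the power of the raw value and the gain is again 7-10 points.
- At ρ 0.7 it is 0.77 SD. Change has 97.3% and 73.7% (SD 1.0 and 1.5) against 98.0% and 76.7% in the same run, a gain of about 1-3 points.

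**6. Where the gain shrinks or reverses.**
- Undetectable Day 0 swabs: if 12-27% are undetectable, the gain over raw Mann-Whitney falls to 1-2 points at ρ 0.3 and 3-15 at ρ 0.5-0.7.
- Missing swabs: with 18 or 16 complete pairs per arm, rank ANCOVA loses 2-5 or 4-12 points.
- All-or-none response: if heparin changes only the chance of responding (30% to 75%), Fisher has 73-74%, Mann-Whitney on change 71-72%, rank ANCOVA 62-70% and raw Mann-Whitney 36-63% (ρ 0.3-0.7).

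**The case against.** The strongest reply is that the sample-size paragraph already implies the primary analysis: the share of patients with a reduction, compared between arms by Fisher's test. On that view the smaller correction is to define the responder and its day. This is a fair reading, and under an all-or-none response Fisher is the more powerful choice. But the plan never says that this is the primary test, and at 20 per arm it does not reach the stated power.

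It is also true that Mann-Whitney can be run on change and that Fisher on a reduction would use Day 0. A reader might infer that no listed between-arm test can use Day 0; the documents do not support that. What is missing is any statement that one of them will.

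A reader might likewise infer that the trial will test every swab at 5%. No such plan is written; it is only not excluded. Nor does the Fisher result show that 40 was miscalculated: the figure reproduces under the normal approximation, and the shortfall arises only if Fisher is the test and 20 per arm are analysed.

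The 12-27% undetectable range may be too high. Entry on clinical suspicion is allowed, but patients not confirmed by RT-PCR within 72 hours of inclusion are withdrawn. Finally, this is a small phase I/II study whose main stated intention is safety, which limits how much rests on the efficacy test but does not remove the gap.

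**Conclusion.** The point holds as an inexpensive improvement. Three facts rest on the documents alone: no primary swab day, no definition of reduction, and no stated use of Day 0 in a between-arm viral-load comparison. The 73.1% Fisher power against the stated 80% follows from the plan's own rates at 20 per arm.

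The rest is conditional. The 10-18% false-positive range needs four separate tests at 5%. The gain from rank ANCOVA needs a uniform shift and a moderate or high Day 0 correlation. It is nil against the raw value at ρ 0, and only about 1-3 points over change at ρ 0.7. A reader might conclude that Day 0 adjustment secures 80% power; without an SD or a correlation in the documents, that cannot be claimed. How the safety and efficacy primaries combine is a separate open question.

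**What to change.** Before unblinding, amend the analysis text as follows.

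1. Name one post-baseline swab day as primary. First reconcile the 7 days of administration in Dosage and administration and in Randomization and study arms with the administration marks on Days 1 to 8 in Table 1, so that the chosen swab has a clear relation to the end of treatment.
2. Name one primary between-arm viral-load test at that swab: rank ANCOVA adjusted for Day 0 viral load, with undetectable values at either swab given the lowest tied rank.
3. Keep the 30% vs 75% responder as the named secondary analysis by Fisher's exact test. Define it as a fall from Day 0 past a stated threshold at the same swab, with a rule for undetectable values, and restate its power as about 73% at 20 per arm.
4. State the analysis population, including patients withdrawn when RT-PCR does not confirm infection, and a rule for patients without the named swab. Call the other swabs supportive and the within-arm Wilcoxon tests descriptive.

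Cost: analysis wording only, since the Day 0 and later quantitative values are already collected; no patient, visit or sample is added. The downsides are a slightly more complex analysis, a missing-swab rule to agree, little gain if the Day 0 correlation is low, and less power than Fisher's test if response is all-or-none.
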